5.6 Handling of Missing/Partial Dates for Adverse Events

If the start or end date for an AE is partially or completely missing, the date will first be queried for resolution if possible. If the year of the start date is missing or the start date is completely missing, the first dose date will be used. If the year of the end date is missing or the end date is completely missing, the event will be regarded as ongoing. Impute AE end date first if both AE start date and end date are partially missing.

If end date of an adverse event is partially missing, impute as follows:

- If the day of the month is missing, the onset day will be set to the last day of the month.
- If the onset day and month are both missing, the day and month will be assumed to be December 31.
- If the imputed end date > death date, then set to death date.

If start date of an adverse event is partially missing, impute as follows:

- If the day of the month is missing, the onset day will be set to the first day of the month unless it is on or after the same month and year as study treatment. In this case, the onset date will be assumed to be the first dose date of treatment or co-therapy, whichever comes first.
- If the onset day and month are both missing, the day and month will be assumed to be January 1 when the year is on or after the year of study treatment. If the year is prior to year of first dose, December 31st will be used. The event onset will be coded to the first dose date of treatment if year is the same as the year of first dose date to conservatively report the event as treatment-emergent.
- If the imputed AE start date is after the AE end date (maybe imputed), then update the AE start date with the AE end date as the final imputed AE start date.
- If the imputed start date > death date, then set to death date
- If the imputed end date is before imputed start date, the AE event will be treated as treatment emergent AE and report it as data issue.

Imputation of partial dates is used only to determine whether an event is treatment-emergent or the duration of the event. A flag will indicate if the start or end date was imputed respectively. Data listings will present the partial date as recorded in the eCRF.

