10.2 Adverse Events

All reported AEs will be coded using the Medical Dictionary for Regulatory Activities (MedDRA) with the most current version for the purposes of summarization. NCI CTCAE Version 5.0 will be used for grading AEs. AEs will be collected and recorded for each patient from the day of signing the ICF until 30 days after last trial intervention administration or until participant started alternative anticancer therapy, whichever is sooner. Prior to receiving trial intervention, only AEs considered related to trial procedures and all SAEs will be summarized by arm, dose level, and dose schedule.

A treatment-emergent adverse event (TEAE) will be defined as any event that was not present prior to the initiation of trial intervention(s) or any event that worsens in either intensity or frequency following exposure to trial intervention(s) through 30 days after cessation of trial treatment, or until the participant starts alternate anti-cancer therapy, or the participant is taking the monotherapy treatment and starts the co-therapy olaparib, whichever occurs first. The exception are RP-3467 related SAEs which were reported until the end of trial and will be included as TEAE regardless of time of onset.

All AEs reports will be summarized by treatment regimen (Arm 1 and Arm 2), dose level and schedule (if applicable) unless otherwise specified.

Overall AE summaries will be presented for the Safety Population (unless otherwise specified). The summaries will include the following categories:

- All TEAEs
- TEAEs with CTCAE Grade 3
- TEAEs with CTCAE Grade 4
- TEAEs with CTCAE Grade 5
- DLT (based on DLT evaluable population)
- RP-3467 related TEAE
 - RP-3467 related TEAE with CTCAE Grade 3
 - RP-3467 related TEAE with CTCAE Grade 4
 - RP-3467 related TEAE with CTCAE Grade 5
- Olaparib related TEAE
 - Olaparib related TEAE with CTCAE Grade 3
 - Olaparib related TEAE with CTCAE Grade 4
 - Olaparib related TEAE with CTCAE Grade 5
- Any Serious AEs
- Any treatment-emergent serious AEs (TESAE)
- RP-3467 related TESAEs
- TEAE leading to dose reduction
- TEAE leading to dose interruption
- TEAE leading to study drug withdrawal
- RP-3467 related TEAE leading to dose reduction
- RP-3467 related TEAE leading to dose interruption

- RP-3467 related TEAEs leading to study drug withdrawal
- Olaparib related TEAE leading to dose reduction
- Olaparib related TEAE leading to dose interruption
- Olaparib related TEAE leading to study drug withdrawal

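### SAP 5.6 has two bullets that act on the same condition when both AE dates are imputed; they give opposite treatment-emergent status for an event that ended before the first dose

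*SAP*

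**What the plan says.** All the rules at issue are in SAP 5.6.

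- **End dates** are imputed first. A missing day becomes the last day of the month; a missing day and month become 31 December.
- **Start dates known only by year:** "The event onset will be coded to the first dose date of treatment if year is the same as the year of first dose date".
- **Reset bullet** (third in the start-date list): if the imputed start "is after the AE end date (maybe imputed), then update the AE start date with the AE end date".
- **Last bullet** of the same list: "If the imputed end date is before imputed start date, the AE event will be treated as treatment emergent AE". Such a record must also be flagged as a data problem.

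The section says that imputation serves only to settle treatment-emergent status or event duration. It does not say which of the two bullets governs.

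SAP 10.2 defines a TEAE as an event that was absent before trial treatment, or one that worsened in intensity or frequency after exposure. SAP 3.2.1 makes the incidence and severity of TEAEs part of the primary endpoint, alongside DLTs.

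**The concern.** Two programmers who follow 5.6 in good faith can classify the same record differently. One codes the reset and derives status from the new start date. The other codes the last bullet as a rule in its own right, which is reasonable because it orders a classification. The second programmer then counts as treatment-emergent an event whose recorded month of resolution lies wholly before the first dose. That event meets neither limb of the 10.2 definition.

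Such records can exist. SAP 10.2 collects AEs from consent, Table 5 calls for procedure-related AEs and SAEs to be reported during Screening, and footnote r of Table 5 schedules a Screening biopsy in Arm 1. At stake is the consistency of the TEAE tables, which report a primary endpoint.

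**Working it through.** The plan gives no figure to reproduce. The check is to apply the rules as written.

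**Inputs.** The imputation rules, the reset bullet and the last bullet come from SAP 5.6, and the TEAE definition from SAP 10.2. The first-dose date in the example is assumed. Let S be the imputed start, E the imputed end and D the first dose.

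**Step 1: the conditions.** The reset acts when S > E and sets S = E. The last bullet acts when E < S and declares a TEAE. When both dates are imputed, these are one inequality.

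**Step 2: an example.** Assume D = 20 March 2025, with the start recorded as 2025 and the end as February 2025. Both dates are partially missing, so the record falls under the list's own heading.

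| Step | Result |
|---|---|
| E (day missing) | 28 February 2025 |
| S (day and month missing, year of first dose) | 20 March 2025 |
| Is S > E? | Yes |
| Reset bullet | S becomes 28 February, before D: not a TEAE |
| Last bullet | TEAE |

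**Step 3: which records are affected.** Take internally consistent records with both dates partially missing and onset within the 30 days before the first dose or later.

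- Start missing only the day: S is the first of its month, or D if that month is the first-dose month or later. E is the end of the same or a later month, or 31 December. So E ≥ S and there is no conflict.
- Start known only by year, the year of the first dose: S = D. An end known only by year gives 31 December, so E ≥ D and there is no conflict. An end known by month, in a month before that of D, gives E < D = S: conflict.

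E is the latest date the recorded month allows. Every conflicting event therefore did end before the first dose.

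**Step 4: enumeration.** The rules were applied to 48 assumed first-dose dates in 2025, onsets from 30 days before to 199 days after the first dose, durations of 0 to 57 days in 3-day steps, and every pattern of missing date parts. With both dates imputed, E < S occurred in 3,058 records with a year-only start and a month-and-year end. It also occurred in 3,336 + 278 = 3,614 records with a wholly missing start. All of these events ended before the first dose, and all were non-TEAE under the reset and TEAE under the last bullet. After the reset, no record still had E < S. The counts depend on the grid and are not expected frequencies; the direction does not depend on it.

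**Step 5: ceiling on the effect.** One participant added to a summary row changes it by 1/n:

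- n = 3 (initial cohort): 1/3 = 33.3 percentage points
- n = 6 (expanded Arm 2 level): 1/6 = 16.7 points
- n = 12 (planned Arm 1, SAP 2.3): 1/12 = 8.3 points

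SAP 10.2 counts a participant once per SOC or PT. The row moves only if that participant has no other event in it.

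**The case against.** **An order is implied.** The reset bullet ends "then update the AE start date with the AE end date as the final imputed AE start date". If that start is final, the last bullet can never act, and it is only a leftover check. The word *final* does suggest this, and Step 4 agrees that nothing remains after the reset. But 5.6 does not say so, and a bullet that can never act would hardly need to order a classification. The parallel sections show the contrast: 5.7 only reports the discrepancy as a data issue, and 5.9 resets and queries. Neither forces a classification. The cross-reference in 10.2 does not help, since it sends the reader to 5.4, on study days.

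**Calling it a TEAE is conservative.** The section invokes conservatism where only the onset year is known and it matches the first-dose year. Here the recorded end month settles that the event was over before dosing.

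**The overlap is narrow.** This stands. A reader might infer that every end-before-start record is in conflict. The text does not support that. With a fully recorded end date only the reset literally applies. A wholly missing start falls under the opening paragraph ("the start date is completely missing, the first dose date will be used"), and it is unclear whether a list headed for partially missing dates applies to it at all.

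**The consequence is limited.** This also stands. Dates are queried before imputation, imputed dates are flagged, listings show the date as recorded, and the analysis is descriptive.

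**Conclusion.** The contradiction is real and small. It affects records with both dates imputed and an imputed end before the first dose; among partially missing dates, Step 3 narrows this to a year-only start with an end month earlier in the first-dose year. For those, the last bullet gives an answer that 10.2 does not allow.

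The number of such records is not known and should be low. The shifts of 33.3, 16.7 and 8.3 points are ceilings for a single row. A reader might infer that each such event moves overall TEAE incidence by that much. It does so only if the participant has no other TEAE at all, and a PT row moves only if there is no other TEAE of that PT.

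A reader might also infer that dose escalation or the MTD is affected. The documents do not support that: BOIN decisions in SAP 2.1 use DLTs, and SAP 10.1 gives these their own window, starting at the first dose, and their own relatedness and toxicity criteria.

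The conclusion assumes internally consistent records and no precedence rule elsewhere in the plan. It is worth correcting because it concerns the derivation of a primary endpoint and costs almost nothing.

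**What to change.** In SAP 5.6:

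1. Keep the reset bullet and add that treatment-emergent status is then derived from the reset start date under 10.2.
2. Delete the treatment-emergent clause from the last bullet, leaving in substance: *where the imputed end falls before the imputed start, apply the reset above and log the record as a data issue.*

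Do not replace the bullet with a rule that makes every event ending on or after the first dose a TEAE. Take a start recorded as April, a first dose on 10 May, an end on 15 May and no worsening. The start imputes to 1 April, so the event was present before treatment and is not a TEAE under 10.2; the end-date rule would make it one.

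The cost is a sentence or two in the SAP and a line of programming, with no change to data collection.

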5.7 Handling of Missing/Partial Dates for Non Anti-cancer Medications/Procedures/Therapy

When the start date or end date of a medication/therapy/procedure, that is not anti-cancer therapy, is partially missing, the date will be imputed to determine whether the medication/therapy/procedure is prior or concomitant. The following rules will be applied to impute partial dates for medications. The first dose date will be the date of the first dose of RP-3467 or olaparib, whichever occurs first.

If the start date of a medication/procedure/therapy is partially missing, impute as follows:

- Medication/procedure/therapy start dates with a missing day and non-missing month will be assumed to have occurred on the first day of the non-missing month if the month and year is after first dose date. If the month and year are prior to the first dose date, the last day of the month will be assigned to the missing day. If the month and year are the same as the first dose date, the first dose date will be used.
- Medication/procedure/therapy start dates with missing day and month will be assumed to have occurred on the first day of the non-missing year (i.e., 01 January) if the year is after the year of first dose date. If the year is prior to the year of first dose date, December 31 will be assigned to the missing fields. If the year is the same as the year of the first dose date, the first dose date will be used.
- If the imputed start date > death date, then set to death date and report it as data issue

If the end date of a medication/procedure/therapy is partially missing, impute as follows:

- Medications/procedure that are not ongoing and have a medication/procedure/therapy stop date with a missing day and non-missing month will be assumed to have stopped on the last day of the non-missing month.
- Medications/procedure that are not ongoing and have a medication/radiotherapy stop date with a missing month will be assumed to have stopped on the last day of the non-missing year (i.e., 31 December).
- If the imputed end date > death date, then set to death date and report it as data issue.
- If the imputed end date is before imputed start date, report it as data issue.

If the year of the start date or the year of the end date of a medication/procedure/therapy is missing, or the start date or end date is completely missing, do not impute.

5.8 Handling of Missing/Partial Dates during Screening Visit

The following rules apply to partially missing dates recorded during the screening visits (e.g. initial diagnosis). If date is completely missing, no imputation is needed:

- If the day of the month is missing, the first day of the month will be used if the year and the month are the same as the first dose of study days. Otherwise, the 15th will be used.

- If the day and month are both missing, the day and month will be assumed to be January 1 when the year is on the year of study treatment. If the year is prior or after the year of first dose date, the date of the first of July will be used, unless other data indicates the date is earlier.

5.9 Handling of Missing/Partial Dates for Prior Anticancer Therapy/Procedures

The following rules will be applied to impute partial dates such as prior systemic anticancer therapy or radiotherapy date (start/end date), or surgery date etc.

Impute end date first. If end date is partially missing, impute as follows:

- If both month and day are missing, then set to December 31
- If only day is missing, then set to the last day of the month
- For prior systemic therapy for cancer, if imputed end date > the first study drug date, then set to the first study drug date
- For prior radiotherapy, if imputed end date > the first study drug date, then set to the first study drug date - 1

If start date is partially missing, impute as follows:

- If both month and day are missing, then set to January 1st
- If only day is missing, then set to the first of the month
- If the imputed start date > end date, then set to the end date (the data should also be queried)

If the year of start date or year of end date of a medication/therapy/procedure is missing, or the start date or end date is completely missing, do not impute.

5.10 Handling of Missing/Partial dates for Post-study Anticancer Therapy/Radiotherapy

For records with completely missing start date, end of treatment date will be used as the start date of post-study therapy/radiotherapy. If the start date of post-study anticancer therapy/radiotherapy is partially missing, impute as follows:

- If the day of the month is missing, the start day will be set to the last day of the month unless it is on the same month and year as last dose of the study treatment. In this case, the start date will be assumed to be the last dose date + 1.
- If the day and month are both missing, the start date will be set to January 1st unless it is on the same year as the last dose date of the study treatment. In this case, the start date will be assumed to be the last dose date + 1.
- If only month is missing, year and day are present, set the missing month to the month of the last dosing date of the study drug unless the day is prior to the last dose day. In this case, impute the missing month as the month of last dose date + 1

No imputation is needed for post-study therapy/radiotherapy end date.

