3.2 Endpoints

3.2.1 Primary Endpoints

- DLTs, incidence and severity of TEAEs

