5.2 Definition of Treatment Emergent Period

Unless otherwise stated, derivations of the worst post-treatment value will be assessed within the confines of the treatment emergent period, defined as the time from the start of study treatment, until 30 days after the last dose of RP-3467 or olaparib, the participant starts a subsequent anti-cancer therapy, or the participant is taking the monotherapy treatment and starts olaparib treatment, whichever occurs first.

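### SAP 5.10 can place an incompletely dated start of post-study anticancer therapy at or just after the last dose, which can close the TEAE window early and drop some recorded post-treatment events

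*SAP*

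**What the plan says.** SAP 3.2.1 gives the primary endpoints as "DLTs, incidence and severity of TEAEs". SAP 10.2 counts an event as treatment-emergent if it arises or worsens "through 30 days after cessation of trial treatment, or until the participant starts alternate anti-cancer therapy", or until a monotherapy participant starts olaparib, whichever comes first. SAP 5.2 likewise closes the treatment-emergent period when "the participant starts a subsequent anti-cancer therapy".

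SAP 10.2 makes one exception to the time limit: "RP-3467 related SAEs which were reported until the end of trial and will be included as TEAE regardless of time of onset".

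SAP 5.10 covers incomplete start dates of post-study therapy:
- Nothing known: "For records with completely missing start date, end of treatment date will be used as the start date of post-study therapy/radiotherapy". The section does not define that date.
- Day missing in the month of last dose, or day and month missing in the year of last dose: "In this case, the start date will be assumed to be the last dose date + 1".
- Day missing, later month: last day of that month.
- Day and month missing, later year: January 1.
- Only the month missing: the month of the last dose, or the next month if the known day falls before the last-dose day.

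For AE onset dates, SAP 5.6 places an event known only by the year of first dose at the first dose "to conservatively report the event as treatment-emergent". SAP 10.2 treats unresolved missing causality as related.

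**The concern.** An early imputed date for new therapy shortens the period in which an event can be a TEAE. AE collection stops when new therapy actually starts (SAP 10.2, Table 5). An AE that the site recorded after the last dose is therefore normally one it judged to precede new therapy. An imputed start of last dose + 1 would override that judgement and take a new or worsening event out of the TEAE tables.

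The imputed date can also conflict with the trial's own schedule. Table 5 footnote b has the EOT visit within 7 days of discontinuation and before subsequent treatment, yet last dose + 1 can fall before that visit.

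The direction matters because the SAP's other safety conventions lean towards counting events. Cohorts are small: the protocol synopsis starts each dose level with up to 3 participants. If one of 3 loses their only event of a given type, that cohort's incidence moves by 1/3, or 33 percentage points.

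**Working it through.** The plan states no figure to reproduce, so the check is date arithmetic on its rules.

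**Inputs.** Window of 30 days after last dose (SAP 5.2, 10.2). Imputation rules (SAP 5.10). EOT visit up to 7 days after discontinuation (Table 5 footnote b). Discontinuation after more than 3 continuous weeks off treatment, with exceptions (protocol synopsis).

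**Formula.** Days of window left = min(30, imputed start − last dose).

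| Missing | Imputed start | Days left of 30 |
|---|---|---|
| Day, month of last dose | last dose + 1 | 1 |
| Day and month, year of last dose | last dose + 1 | 1 |
| Whole date | end of treatment date | 0 if that is last dose; 7 if an EOT visit 7 days later; about 21 + 7 = 28 after a 3-week hold |
| Day and month, later year | January 1 | 30 for last doses up to 2 December; 29 (3 December) down to 1 (31 December) |
| Day, later month | last day of that month | 28 to 30 for true starts within 30 days of last dose; never shorter than the true window |

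The month-only rule depends on the known day. In the year of last dose it takes the earliest month that fits, so it also leans early.

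**Size of the loss under last dose + 1.** Loss = min(30, true start − last dose) − 1.
- Last dose 2 June, therapy known only as June: the true start is 30 June at the latest, 28 days on. Maximum loss = 28 − 1 = 27 days.
- Last dose 1 March, only the year known: the true start could be 31 December, 305 days on, so the full window should stand. Loss = 30 − 1 = 29 days, the ceiling for this rule.

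**Average rather than maximum.** The documents give no distribution of start dates. I assumed every last-dose date in 2025, with true starts spread evenly over 1 to 30 days later.

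| Branch | Mean window under 5.10 | Mean true window | Too short | Too long |
|---|---|---|---|---|
| Day missing, same month | 1.0 | 10.5 | 93.4% | 0% |
| Day and month missing, same year | 1.0 | 15.3 | 96.5% | 0% |
| Day and month missing, later year | 10.7 | 20.3 | 93.5% | 0% |
| Day missing, later month | 30.0 | 20.3 | 0% | 93.5% |

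The mean loss is 10.5 − 1 = 9.5 days in the first branch and 15.3 − 1 = 14.3 in the second. When only the day is missing, 49% of combinations fall in the same month and 51% in a later one, so the net direction for that pattern is mixed.

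**Which events are exposed.** Those with onset or worsening after the imputed date: non-serious AEs, SAEs not attributed to trial treatment, and SAEs attributed to olaparib alone.

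**The case against.** The strongest objection is that SAP 5.10 never says its dates set the TEAE cut-off. The link is inferred because no other visible rule supplies the date, and SAP sections 7 to 9 are not in the public text, so a limit on its use could stand there. That is a fair reservation, and it is a reason for the SAP to say which use is meant.

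Frequency is also open. A Safety Follow-up visit takes place at 30 (+14) days, and sites must know when new therapy starts in order to stop AE collection, so starts inside the window may be well dated. Against this, post-trial therapy is collected at long-term follow-up, often by telephone, at 3 to 24 months. The documents do not settle how often dates will be incomplete.

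A reader might infer several stronger things that the documents do not support:
- That the whole primary endpoint is affected. DLTs have their own Cycle 1 window (SAP 10.1).
- That all late events are lost. RP-3467-related SAEs stay TEAEs, toxicity that began on treatment is already counted, and SAP 10.2 still lists every AE by participant.
- That laboratory shift tables certainly lose values. SAP 10.3 refers to the treatment-emergent period but also admits visits up to 30 days past last dose, so the effect is uncertain.
- That every branch undercounts. The later-month rule lengthens the window, and the January 1 rule shortens it only for last doses on 3 to 31 December.
- That 5.10 contradicts 5.6. The two sections impute different dates; they differ in direction and are not in conflict.

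**Conclusion.** The point holds in a limited form. If SAP 5.10 supplies the date that ends the TEAE window, its last dose + 1 rules cut 30 days to 1. Its rule for a completely missing date leaves between 0 and about 28 days, depending on an undefined term. In these branches some recorded new or worsening events, other than RP-3467-related SAEs, can lose TEAE status. This runs against the conservative lean of SAP 5.6 and of the missing-causality rule in 10.2.

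Under last dose + 1 the loss reaches 29 days at most. It would be 30 only for a completely missing date with end of treatment read as last dose. Neither figure is typical: with evenly spread start dates, an assumption, the mean loss under last dose + 1 is about 9.5 to 14.3 days. The number of participants affected cannot be estimated from the documents. The analysis is descriptive, so no test or error rate is involved; the issue is a possible undercount in the TEAE tables.

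**What to change.** Add to SAP 5.10, in substance: *For the treatment-emergent period and TEAE derivation only, a partial start date of subsequent anticancer therapy is imputed to the latest date consistent with its known parts. A completely missing start date does not truncate the window, which then runs to 30 days after last dose. The cut at the start of olaparib for monotherapy participants is unchanged.*

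The present imputation may stay for any other use, with end of treatment date defined. SAP 5.2 and 10.2 should point to the new text, and SAP 10.3 should say which window governs the shift tables.

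The cost is one short paragraph and a second imputed-date variable. The downside is that a few events after the actual start of new therapy may count as TEAEs. That is limited, because AE collection stops at that start.
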